5 STUDY TREATMENTS

5.1 Study Drug

Bexagliflozin tablets, 20 mg, are prolonged release, blue caplet-shaped, film-coated tablets that are intended for use in investigational studies in humans. The tablets contain excipients designed to promote extended release through a gastroretentive mechanism. The tablets exhibit a > 75% release of drug substance by 8 hours in simulated gastric fluid *in vitro*.

5.2 Treatments Administered

Subjects who consent to participate and meet all inclusion/exclusion criteria will receive a single oral dose of bexagliflozin tablets, 20 mg.

5.3 Selection and Timing of Dose for Each Subject

Subjects in the hepatic impairment group will be dosed first. Control subjects will be enrolled after at least one subject in the hepatic impairment group is enrolled. Each control subject will be matched with individual subject in hepatic impairment group. Each subject will receive a single oral dose of bexagliflozin tablets, 20 mg, with 240 mL of water on Day 1 (D1) after an overnight fast of at least 10 h.

5.4 Method of Assigning Subjects to Treatment Groups and Sequences

This is an open-label, parallel-group study. An adequate number of male or female subjects with moderate hepatic impairment [Child-Pugh total score 7-9] will be enrolled to obtain eight evaluable subjects. Another adequate number of healthy subjects with normal hepatic function will be enrolled to obtain at least 8 evaluable subjects who are matched with the subjects in the moderate hepatic impairment group individually for age (± 10 years), weight ($\pm 10\%$), sex, and smoking status.

Subjects who withdraw early for safety reasons will not be replaced.

5.5 Blinding

This is an open-labeled study.

5.6 Concomitant Therapy

Participants in the healthy control group will be prohibited from taking any prescription or OTC drugs, supplements, or vitamins 7 days prior to D0, as well as for the duration of the study. Subjects in the hepatic impairment group must not have changed the dose or frequency of administration of any prescription medications for 30 days prior to D0.

Medications may be prescribed for management of an adverse event (AE). Subjects may receive any medications for AEs that are necessary to treat the event or minimize the

likelihood of having serious adverse events (SAEs) in the investigators' judgment. Concomitant medications administered during the study are to be recorded on the case report form (CRF). The medication name, dose, frequency, route of administration, date(s) of administration and reason for administration shall be recorded. This documentation shall continue until the end of the study.

5.7 Restrictions

5.7.1 Prior Therapy

No study subject shall have been dosed with any SGLT2 inhibitor within 3 months prior to D0, nor with an investigational drug within 30 days or 5 half-lives. No subject shall have previously participated in a bexagliflozin clinical trial. No subject in the control group shall have taken any OTC drugs, vitamins, or supplements 7 days prior to D0 or shall have consumed caffeine or similar methylxanthine-containing foods/beverages (tea, hot chocolate, energy drinks) within 48 h prior to D0. Subjects in the hepatic impairment group must not have changed the dose or frequency of administration of any prescription medications for 30 days prior to D0.

5.7.2 Fluid and Food Intake

Bexagliflozin will be administered to subjects after an overnight fast of at least 10 h with approximately 240 mL water. Subjects should fast at least 8 h prior to any safety laboratory collection. Water will be allowed as desired except for one hour before and after drug administration.

5.7.3 Subject Activity Restrictions

Alcohol consumption is restricted for 72 hours prior to D0 and throughout the study.

5.8 Treatment Compliance

To ensure compliance, all medication dosing will be supervised by the Investigator or qualified staff in the clinic. The exact times of dosing will be recorded in the CRFs, including a record of drug administration checks followed by hand and mouth inspection.

5.9 Packaging and Labeling

Bexagliflozin tablets, 20 mg, are packaged in high-density polyethylene bottles sealed with a child resistant closure. The product is packaged in 90 count bottles.

Investigational product bottles will be labeled with the protocol number, drug name and strength, lot number, sponsor's name, storage condition, and the investigational drug caution statement.

5.10 Storage and Accountability

Bexagliflozin tablets will be stored below 30°C (86°F) in a secure area with access limited to authorized personnel. The pharmacist shall maintain an inventory of bexagliflozin product and the number of tablets dispensed per study subject. A reconciliation of drug inventory will be performed at the end of the study and the results of this inventory shall be recorded in the Drug Consumption Form (or equivalent). Empty, partially used and unused bottles must be returned to the depot for destruction at study close out, after the Drug Consumption Form (or equivalent) is completed.

6 STUDY PROCEDURES

6.1 Informed Consent

Before each subject is enrolled in the clinical study, written informed consent will be obtained from the subject according to the regulatory and legal requirements. As part of this procedure, the investigator or designee must explain orally and in writing the nature, duration, and purpose of the study, and the action of the drug in such a manner that the study subject is aware of the potential risks, inconveniences, or AEs that may occur. The investigator should educate potential subjects about the scientific importance of their data and the vital role that their participation has for the outcome of the entire study. The subject must be informed that he/she is free to withdraw from the study at any time. He/she will receive all information that is required by federal regulations and International Council for Harmonisation (ICH) guidelines.

The informed consent document must be signed and dated. One copy will be given to the subjects, and the investigator will retain a copy as part of the clinical study records. The investigator will not undertake any investigation specifically required for the clinical study until written consent has been obtained. The terms of the consent and when it was obtained must also be documented.

6.2 Medical History

The following information will be collected at the screening visit:

- Demographic information including age, sex, and race.
- Significant medical and surgical history with documentation of the dates relative to the time of study screening, if applicable.
- History of clinically significant allergies including to drugs and latex.
- History of smoking.
- History of blood donation within two months or blood components or plasma donation in the 14 days prior to D0.
- History of vaccination within 30 days prior to D0.
- History of diagnosis of HIV.
- History of severe or moderate renal dysfunction or a history of kidney, other organ, bone marrow or stem cell transplant.
- History of Hepatitis B, or Hepatitis C virus infection.
- History of exposure to any investigational drug in the previous 30 days or 5 half-lives prior to D0, whichever is longer.
- History of exposure to any SGLT2 inhibitors in the last 3 months prior to D0.
- History of participation in any bexagliflozin clinical trial.
- Medication history including prescription, OTC drugs, and vitamin preparation or supplement use (including St. John's Wort and ginseng) within 7 days or 5 half-lives of

the drug, whichever is longer, prior to D0 (**for subjects in the healthy control group only**).

- A history of any change in dose or frequency of dosing of prescription medication within 30 days prior to D0 (**for subjects in hepatic impairment group only**)

6.3 Physical Examination

The investigator or designated qualified individual will perform the PEs. A complete PE will be performed at screening, and on clinic admission (D0). A partial PE will be performed on day 1, and at follow up visit as described in [Appendix 1](#).

A complete PE will include body weight, height and general assessment of all body systems including the skin, head, eyes, ears, nose, throat, neck, lungs, heart, abdomen, lymph nodes, and extremities. A partial PE will include a general assessment of the skin, heart, lungs and abdomen.

6.4 Vital Signs

Vitals signs (VS), including pulse, systolic and diastolic blood pressure (BP), respiration rate, and oral cavity temperature, will be measured on scheduled visits as described in [Appendix 1](#).

Vital signs, including pulse, systolic and diastolic BP, shall be measured prior to blood draws and after a subject has been sitting for 5 minutes.

Respiration rate should be measured after at least 5 minutes of rest.

BP measurements will be obtained using a calibrated manual or oscillometric sphygmomanometer.

6.5 Electrocardiography

A 12-lead electrocardiography (ECG) will be conducted as listed in [Appendix 1](#) and whenever clinically indicated.

The data should be collected from the subject in the supine position after at least 5 minutes of rest. ECG parameters measured will be the RR interval, PR interval, QRS duration, and QT. Each ECG shall also be assessed by the investigator for signs of ischemia, clinically significant hypertrophy, and clinically significant T-wave abnormalities.

It is the investigator or designee's responsibility to review the results of the ECG as they become available. For each abnormal ECG result, the investigator shall ascertain if the abnormality represents a clinically significant change from the screening ECG for that individual subject. This determination, however, need not be made the first time an abnormal result is observed. The investigator may repeat the ECG to verify the results of the original

result. If the ECG result is determined to be a clinically significant and abnormal change from baseline for that subject, the finding shall be considered an AE.

6.6 Clinical Laboratory Tests

6.6.1 Laboratory Parameters

Subjects will be in a seated, semi-recumbent or supine position during blood collection. Clinical blood chemistry and hematology tests will be performed at the scheduled visits ([Appendix 1](#)). Blood samples shall be drawn after overnight fasting (at least 8 h). The details of the required laboratory tests are listed in Table 1.

Table 1. Required Laboratory Tests

Test Name	mL (sample)
Hematology	
	8.5 (blood)
Hematocrit	Mean corpuscular volume
Hemoglobin	Platelet count
Mean corpuscular hemoglobin	Red blood cell count
Mean corpuscular hemoglobin concentration	White blood cell count with differential
International normalized ration (INR)	
Serum Chemistry, Electrolytes and Lipids	
	4.0 (blood)
Albumin	Calcium
Alanine aminotransferase (ALT)	Magnesium
Aspartate aminotransferase (AST)	Alkaline Phosphatase (ALP)
Blood urea nitrogen (BUN)	Phosphorus
Glucose	Potassium
Bicarbonate	Sodium
Creatinine	Total bilirubin
Creatinine kinase	Direct bilirubin
Chloride	Uric acid
Total protein	Total cholesterol
Low-density lipoprotein cholesterol, calculated	High-density lipoprotein cholesterol
Triglycerides	
Urinalysis	
	20 (urine)
Appearance	Nitrite
Bilirubin	pH
Color	Occult blood
Glucose	Protein
Ketones	Specific gravity
Microscopic examination will be performed if protein, leukocyte esterase, nitrite, or blood is positive	Urobilinogen
	Leukocyte esterase

Table 1. Required Laboratory Tests

Test Name	mL (sample)
Urine Drug Screen	10 (urine)
Amphetamines	Opiates
Barbiturates	Benzodiazepines
Cocaine Metabolites	Cannabinoids (THC)
MDMA	Methamphetamine
TCA	Methadone
PCP	OXY
	Alcohol
Urine pregnancy test (Female only)	5.0 (urine)
Infectious Disease Testing (measured at screening only)	4.0 (blood)
Hepatitis B surface antigen (HBsAg)	Hepatitis C virus (HCV)
Human Immunodeficiency Virus antibody (HIV)	

6.6.2 Sample Collection, Storage, and Shipping

6.6.2.1 Hematology and Blood Chemistry

Blood samples for hematology and chemistry will be collected. Timing of sample collection is described in [Appendix 1](#).

6.6.2.2 Urinalysis

Clean-catch, midstream urine samples will be collected per the schedule outlined in Section 7 and in [Appendix 1](#). Dipstick urinalysis will be conducted at the local laboratory. If protein, leukocyte esterase, nitrite or blood is positive in the dipstick analysis, a microscopic examination will be performed. If microscopic examination is suggestive, then a culture may be performed at the discretion of the investigator. In addition, unscheduled urinalysis will be performed from a clean-catch urine sample from subjects with symptoms of UTI or pyelonephritis.

6.6.2.3 Urine Collection for PD

Predose urine samples must be collected from -12 to 0 h for baseline measurement. Subjects will empty their bladders prior to dosing. Postdose urine will be collected without preservative in four (4) batches at 0-12, 12 to 24, 24 to 36, and 36 to 48 h after oral administration of bexagliflozin. Urine must be refrigerated at 2-8 °C during collection. After collection, the total volume of each batch and collection time will be recorded. A 20 mL aliquots of the urine at each batch will be prepared from well-mixed urine collections. One aliquot of the urine samples will be analyzed for urinary glucose and creatinine at the local lab (for PD analysis).

6.6.2.4 Plasma Sample Collection for PK

Whole venous blood samples of 6 mL will be collected from a peripheral vein at predose and at 0.5, 1, 2, 3, 4, 5, 6, 8, 10, 12, 16, 24, 36, and 48 h after oral administration of bexagliflozin. Blood samples will be collected in tubes containing potassium ethylenediaminetetraacetic acid (K₂EDTA) and stored on ice until centrifuged under refrigeration for at least 10 min at 3,000 rpm. After centrifugation, plasma will be removed, divided into 3 aliquots of approximately 1.0 mL, frozen and stored at or below -20 °C. Plasma should be processed and frozen within 2 h of blood collection. Processed frozen plasma samples will be transferred on dry ice to the analytical laboratory and will be stored at or below -20 °C until LC-MS/MS analysis and protein binding determination.

6.6.3 Blood Volume and Frequency for PK and Safety Assessment

The approximately total volume and number of sampling times for blood collections are outlined in Table 2.

Table 2. Blood Samples

Test	Volume per sample (mL)	No. of Samples	Total*	Storage
Blood				
Hematology	8.5	5	42.5	4 °C
Chemistry and infectious disease testing	4	6	24	4 °C
Virology testing	7	1	7	4 °C
PK	6	15	90	-20 °C

*Total blood volume required in each subject: approximately 178.5 mL, including additional 15 mL blood for heparin locks for PK draws.

6.7 Adverse Events Assessments

Adverse Event (AE): Any untoward medical occurrence in clinical investigation subject administered a pharmaceutical product. An AE does not necessarily have to have a causal relationship with this treatment.

An AE can therefore be any unfavorable and unintended sign (including an abnormal laboratory finding, for example), symptom, or disease temporally associated with the use of an investigational product, whether or not it is considered related to the investigational product.

Serious Adverse Event (SAE): A serious adverse event (experience) or reaction is any untoward medical occurrence that at any dose:

- results in death,

- is life-threatening (*NOTE: The term "life-threatening" in the definition of "serious" refers to an event in which the patient was at risk of death at the time of the event and does not refer to an event which hypothetically might have caused death if it were more severe.*),
- requires inpatient hospitalization or prolongation of existing hospitalization,
- results in persistent or significant disability/incapacity,
- is a congenital anomaly/birth defect,
- is an important medical event.

An important medical event is an event that may not be immediately life-threatening or result in death or hospitalization but may jeopardize the patient or may require intervention to prevent one of the other outcomes listed in the definition above. Examples of such events are intensive treatment in an emergency room or at home for allergic bronchospasm, blood dyscrasias or convulsions that do not result in hospitalization, or development of drug dependency or drug abuse.

Non-serious adverse events are all events that do not meet the criteria for a "serious" adverse event.

Immediately Reportable Adverse Event (IRAE): Any serious adverse event or any adverse event that necessitates discontinuation of investigational product.

Clinical Laboratory Changes: It is the investigator's responsibility to review the results of all laboratory tests as they become available. For each abnormal laboratory test result, the investigator needs to ascertain if this is a clinically significant change from baseline for that individual subject. This determination, however, does not necessarily need to be made the first time an abnormal value is observed. The investigator may repeat the laboratory test or request additional tests to verify the results of the original laboratory tests. If this laboratory value is determined to be a clinically significant change from baseline for that subject, this is considered an AE.

Hypoglycemia will be defined as any fasting plasma glucose (FPG) value ≤ 70 mg dL⁻¹ and documented as described in [Section 6.7.3.4](#).

Any clinical significant increase in hepatic enzymes and specifically ALT or AST $>$ or $= 3x$ ULN (for healthy control subjects), or AST or ALT $>$ or $=$ to $3x$ the subject's baseline values, whichever is greater will be considered a clinical laboratory adverse event.

An increase in creatinine from baseline by 0.5 mg dL⁻¹ or more will be reported as a laboratory adverse event.

Severity: Adverse events will be graded on a 3-point scale and reported as indicated on the CRF. The intensity of an adverse experience is defined as follows:

1 = Mild: discomfort noticed, but no disruption to daily activity

2 = Moderate: discomfort sufficient to reduce or affect normal daily activity

3 = Severe: inability to work or perform normal daily activity

Investigational Product Causality: The site and database should ask for the causality relative to the study compound. Relationship of an adverse event to dosing will be assessed as follows:

Definite: There is a reasonable causal relationship between the investigational product and the AE when the event responds to withdrawal of the investigational product (dechallenge), and recurs with administration of the investigational product (rechallenge).

Probable: There is a reasonable causal relationship between the investigational product and the AE. The event responds to dechallenge. Rechallenge is not required.

Possible: There is a reasonable causal relationship between the investigational product and the AE. Dechallenge is lacking or unclear.

Not Likely: There is a temporal relationship to investigational product administration, but there is not a reasonable causal relationship between the investigational product and the event.

Unrelated: There is no temporal or causal relationship to investigational product administration.

6.7.1 Collecting and Reporting Adverse Events

Adverse event data collection will begin on the first clinical admission day. The investigator will periodically assess subjects for the occurrence of adverse events. To avoid bias in collecting information about adverse events, the investigator should ask subjects the following question: "How have you felt since you were last checked?" All adverse events (serious and non-serious) reported by the subject must be recorded on the source documents and CRFs provided by the sponsor.

In addition, the study Medical Monitor or the designated Sponsor personnel must be notified immediately by telephone or email of any immediately reportable adverse events according to the procedure outlined below. Special attention should be paid to recording hospitalization and concomitant medications.

6.7.2 Immediately Reportable Adverse Events

The investigator must report any SAE, by telephone, email, or fax, to Theracos or its representative immediately after the investigator becomes aware of the event. An IRAE form should be completed and sent by email, fax or overnight courier to the sponsor within 24 h of knowledge of the event.

Non-serious events that require discontinuation of investigational product (including laboratory abnormalities) should be reported to Theracos within 3 working days. The IRAE form should be completed and sent by email, fax or overnight courier to the sponsor.

Subjects experiencing an SAE should be followed clinically until their health has returned to baseline status or until all parameters have returned to normal, or have otherwise been explained. It is expected that the investigator will provide or arrange appropriate supportive care for the subject.

6.7.3 Follow-up of Adverse Events

6.7.3.1 Follow-up of Non-serious Adverse Events

Non-serious adverse events that are identified on the last scheduled contact must be recorded on the AE CRF with the current status noted. All non-serious events that are ongoing at the time will be recorded as ongoing on the CRF.

6.7.3.2 Follow-up of Post-Study Serious Adverse Events

SAEs that are identified on the last scheduled contact must be recorded on the AE CRF page and reported to Theracos according to the reporting procedures outlined in [Section 6.7.1](#). These may include unresolved previously reported SAEs, or new SAEs. The investigator should follow these subjects until the events are resolved, or the subject is lost to follow-up. Resolution means the subject has returned to the baseline state of health, or the investigator does not expect any further improvement or worsening of the subject's condition. The investigator should continue to report any significant follow-up information to Theracos until the event has been resolved.

Any new SAEs reported by the subject to the investigator that occur after the last scheduled contact, and are determined by the investigator to be reasonably associated with the use of the investigational product, should be reported to the Medical Monitor or the sponsor's designated personnel. These may include SAEs that are captured on follow-up telephone contact or at any other time point after the defined study period (i.e., up to last scheduled contact). The investigator should follow subjects with SAEs identified after the last scheduled contact until the events are resolved, or the subject is lost to follow-up. The investigator should continue to report any significant follow-up information to the Sponsor until the event has been resolved. This study requires that subjects be actively monitored for SAEs for at least 14 days after discharge from the study.

6.7.3.3 Hepatotoxicity

Any clinical significant increase in hepatic enzymes and specifically ALT or AST $>$ or $=$ 3x ULN (for healthy control subjects), or AST or ALT $>$ or $=$ to 3x the subject's baseline values, whichever is greater, requires immediate repeat test within 48 to 72 h to confirm the hepatic enzyme elevation. The event should be reported as an adverse event within the CRF if the enzyme elevation is confirmed or worsening. Potential contributors to hepatic enzyme elevation should be evaluated by the investigator. The investigator is encouraged to consult with the Medical Monitor regarding ongoing diagnostic workup.

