24. If destined for the hepatic impairment group, a history of fluctuating or rapidly deteriorating hepatic function or the production of widely varying or worsening clinical and/or laboratory signs of hepatic impairment within the screening period
25. If destined for the healthy control group, a history of prescription or over-the-counter (OTC) drug use within 7 days or 5 half-lives of the drug, whichever is longer, prior to D0
26. If destined for the healthy control group, a history of liver disease or liver injury as indicated by an alanine aminotransferase (ALT), aspartate aminotransferase (AST), > 2.5 × the upper limit of normal (ULN) at screening, or serum bilirubin > 1.5 × ULN
27. If destined for the healthy control group, evidence of HBV or HCV infection.
28. Any other serious medical condition that, in the opinion of the investigator, would pose a significant risk to the subject or interfere with the interpretation of safety, PK, or PD data.

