6.3.4 Laboratory Data

Clinical laboratory tests on hematology, serum chemistry, and urinalysis will be performed according to the schedule in Section 3.6. Investigators will assess whether there are any clinically significant abnormalities and record the abnormality on medical history or AE forms.

Conversion to the International System of Units

All laboratory data will be stored in the database with the units in which they are originally reported. Laboratory data in summary tables and subject data listings will be presented in the International System of Units (SI units; *Système International d'Unités*). Laboratory data not reported in SI units will be converted to SI units before further processing or data analysis.

Abnormal Values

Based upon laboratory normal ranges, laboratory test results will be categorized according to the normal range as low, normal and high. Subjects with laboratory data outside the normal range will be listed with abnormal values flagged.

Table 3 Clinical Laboratory Tests

Hematology	
Hematocrit (Hct)	Mean corpuscular volume (MCV)
Hemoglobin (Hgb)	Platelet count
Mean corpuscular hemoglobin (MCH)	Red blood cell (RBC) count
Mean corpuscular hemoglobin concentration (MCHC)	White blood cell (WBC) count with differential
International normalized ration (INR)	
Serum Chemistry, Electrolytes, and Lipids	
Albumin (ALB)	Calcium (Ca)
Alanine aminotransferase (ALT)	Magnesium
Aspartate aminotransferase (AST)	Phosphorus
Blood urea nitrogen (BUN)	Potassium (K)
Glucose	Sodium (Na)
Bicarbonate	Total bilirubin
Creatinine	Direct bilirubin
Creatinine kinase	Alkaline Phosphatase (ALP)
Chloride (Cl)	Uric acid
Total protein	Low-density lipoprotein cholesterol (LDL-C), calculated
Total cholesterol (TC)	
High-density lipoprotein cholesterol (HDL-C)	
Triglycerides (TG)	
Urinalysis	
Appearance	Nitrite
Bilirubin	pH
Color	Protein
Glucose	Specific gravity
Ketones	Urobilinogen
Microscopic examination of sediment (performed if protein, leukocyte esterase, nitrite, or blood is positive)	Leukocyte esterase
Occult blood	
Urine Collection	
Glucose	Creatinine
Urine Drug Screen	

Amphetamines	Opiates
Barbiturates	Benzodiazepines
Cocaine Metabolites	Cannabinoids
MDMA	Methamphetamine
TCA	Methadone
PCP	OXY
Alcohol	

Pregnancy Test - Urine

Infectious Disease Testing (measured at screening only)

Hepatitis B Surface Antigen (HbsAg)	Hepatitis C virus (HCV)
Human Immunodeficiency Virus antibody (HIV)	

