8.4.1 Adverse Events

All AEs will be coded to system organ class (SOC), and preferred term (PT), using the latest Medical Dictionary for Regulatory Activities coding dictionary (version to be specified in the clinical study report). All reported AEs will be listed, but only TEAEs will be summarized.

The incidence of all TEAEs will be summarized by hepatic function group. In the summary tables, subjects may be counted under multiple SOCs and PTs, but for each SOC and PT, subjects are only counted once. If a subject has the same AE on multiple occasions, the highest severity (severe > moderate > mild) or drug relationship (definite > probable > possible > not likely related > unrelated) recorded for the event will be presented. If severity is missing, subjects will be included as missing (for severity). If drug relationship is missing, subjects will be included in related tables (e.g., considered treatment related [TR]). Summary tables will be organized by SOC, then PT.

The following summaries will be presented for TEAEs for each hepatic function group and for all subjects for selective summaries for the Safety Population.

- Overall Summary of TEAEs by hepatic function group
- Incidence of TEAEs by hepatic function group, system organ class, and preferred term
- Incidence of Treatment Emergent Serious Adverse Events by hepatic function group, system organ class, and preferred term

Subjects who prematurely withdraw due to TEAEs and subjects with serious TEAEs will be listed for the Safety Population.

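### Protocol 6.7 and 6.7.3.3 apply different adverse event rules to the same ALT/AST rise, and the shared threshold sentence has more than one reading for controls

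*Protocol*

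**What the plan says.** Protocol 6.7, under clinical laboratory changes, sets a numeric trigger for liver enzymes: ALT or AST at least 3x ULN, marked for healthy controls, or at least 3x the subject's own baseline. The sentence opens with a clinical-significance qualifier and ends "whichever is greater will be considered a clinical laboratory adverse event". It contains no confirmation step.

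The general text earlier in the same paragraph group is looser. On judging whether an abnormal value is a clinically significant change, it says: "This determination, however, does not necessarily need to be made the first time an abnormal value is observed". It adds: "The investigator may repeat the laboratory test or request additional tests to verify the results of the original laboratory tests".

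Protocol 6.7.3.3 repeats the trigger in nearly the same words but attaches a different consequence. A rise at the threshold "requires immediate repeat test within 48 to 72 h to confirm the hepatic enzyme elevation", and then: "The event should be reported as an adverse event within the CRF if the enzyme elevation is confirmed or worsening".

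Exclusion criterion 26 in Protocol 4.3 bears on the control threshold. It begins "If destined for the healthy control group, a history of liver disease or liver injury as indicated by" and sets the ALT/AST limit at more than 2.5x ULN at screening, so a control at up to 2.5x ULN can enter.

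SAP 6.3.4 leaves recording to judgement: "Investigators will assess whether there are any clinically significant abnormalities and record the abnormality on medical history or AE forms". It gives no 3x threshold and no confirmation rule. SAP 8.4.1 lists among its tables: "Incidence of TEAEs by hepatic function group, system organ class, and preferred term". SAP 8.4.2 separately summarizes laboratory values and changes from baseline, and lists and flags out-of-range results.

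**The concern.** The two protocol sections start from the same laboratory finding and can end with different entries on the adverse event form. A site working from 6.7 records the event once the rise is judged clinically significant. A site working from 6.7.3.3 waits for the repeat and records it only if the rise holds or worsens. The SAP tables count what was recorded, so the count of liver-enzyme events can depend on which section a site followed. Protocol 4.1 speaks of investigational sites in the plural, so uneven application is possible.

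Safety and tolerability in hepatic impairment is the secondary objective, and transaminases are an obvious thing for a reader of this trial to look at. With groups of eight, a single reclassified subject shows in a percentage table.

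A second, separate ambiguity sits inside the trigger sentence that both sections share. It assigns the ULN limb to controls and then asks for the greater of two quantities, which leaves the control threshold open to two readings.

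**Working it through.** The plan states no figure to reproduce, so the check is mainly a comparison of text.

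**Step 1. Same trigger, three possible courses.** Take a subject whose ALT or AST reaches the threshold and whose rise is judged clinically significant.

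| Course | Protocol 6.7 | Protocol 6.7.3.3 |
|---|---|---|
| Repeat at 48 to 72 h confirms or shows worsening | adverse event | adverse event |
| Repeat does not confirm | adverse event | not reported |
| No repeat obtained | adverse event | reporting condition not met |

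The sections agree in the first row and differ in the other two. On the same threshold, the 6.7 count can equal or exceed the 6.7.3.3 count but cannot fall below it.

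**Step 2. Does the SAP choose?** No. SAP 6.3.4 relies on investigator judgement, and SAP 8.4.1 tabulates treatment-emergent events as recorded. Neither refers to 6.7 or 6.7.3.3 for enzyme rises.

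**Step 3. Size.** Input: eight subjects per group (Protocol 3.1). SAP 6.3.3.4 counts a subject once per preferred term. If one subject falls in the second or third row and has no other event under that term, the group's incidence for that term differs between the rules by

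1/8 = 0.125 = 12.5 percentage points,

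for example 0/8 (0%) against 1/8 (12.5%). The documents give no expected rate of unconfirmed 3x rises, so no expected number of affected subjects can be computed.

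**Step 4. Control threshold.** Let *b* be a control's baseline ALT or AST as a multiple of ULN.

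- Reading A, in which the parenthesis assigns the ULN limb to controls: trigger = 3x ULN.
- Reading B, in which controls take the greater of the two limbs: trigger = max(3, 3*b*) x ULN.

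For *b* ≤ 1, both give 3x ULN. For *b* > 1, reading B gives 3*b* x ULN. At the entry limit, *b* = 2.5:

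3 × 2.5 = 7.5x ULN, and 7.5/3 = 2.5.

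The readings therefore differ by a factor of *b*, up to 2.5. This takes baseline as equal to the screening value. Exclusion 26 applies at screening, whereas the SAP defines baseline as the last assessment before dosing.

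**The case against.** The best reply is that 6.7.3.3 is simply the working procedure for 6.7. The 6.7 sentence covers only clinically significant rises, and the general text around it lets the investigator repeat a test before deciding. On that view the repeat informs the judgement, and an unconfirmed rise was never clinically significant. It can be added that 6.7.3.3 does not say in terms that an unconfirmed rise must be left unreported.

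Part of this stands. It would be wrong to say that 6.7 makes every threshold rise an event automatically. But the repeat in 6.7 is optional, while in 6.7.3.3 it is mandatory and decides reporting. The ALT/AST sentence refers neither to the general text nor to 6.7.3.3. The condition in 6.7.3.3 has a purpose only if unconfirmed rises are not reported.

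On the threshold, the reply is that a coherent reading exists (controls: the greater of the two limbs; impaired subjects: 3x baseline) and that for a control with baseline at or below ULN the two readings coincide. That is correct. The gap opens only above ULN, and 7.5x ULN needs a control at the entry limit who still counts as being in good general health.

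Four stronger inferences are tempting, and the documents do not support them:

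- **A key liver safety count is compromised.** No liver endpoint or hepatotoxicity table is named, and SAP 3.3 rules out formal hypothesis testing. Under SAP 8.4.2 the enzyme values are summarized, and out-of-range results listed and flagged, whatever their adverse event status.
- **A rise at 48 h that has resolved by Day 15 is classified differently.** The deciding test in 6.7.3.3 is the 48 to 72 h repeat, not the Day 15 sample. A rise confirmed at the repeat is an event under both sections, even if normal by Day 15.
- **The schedule contradicts the repeat requirement.** A repeat after the Day 3 sample would fall on Day 5 to 6 (Day 3 plus 2 to 3 days), when no visit is planned. A for-cause test need not appear in the visit schedule, however; 6.7 allows additional tests and SAP 6.1.1 has rules for unscheduled visits.
- **The two groups are not comparable.** Both are under the same two sections, and nothing suggests that staff would apply different sections by group.

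**Conclusion.** The inconsistency is real but minor. Two protocol sections give different recording rules for the same ALT/AST trigger, and the SAP does not settle which one its tables reflect. The effect is confined to rises that the repeat does not confirm or that are never repeated. Each such subject moves a group's preferred-term incidence by 12.5 percentage points. That assumes eight subjects per group and no other event under the same term for that subject. How often this would happen cannot be judged from the documents.

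The threshold ambiguity is also real, and it affects only controls with baseline above ULN. The two readings are 3x ULN and up to 7.5x ULN, the upper figure assuming a baseline at the 2.5x ULN entry limit.

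The consequence is uncertainty over what an entry in the adverse event tables means. The underlying laboratory data are not lost.

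**What to change.** Reconcile Protocol 6.7 and 6.7.3.3 so that one rule decides when an ALT/AST rise is recorded as an adverse event, applied in the same way in both groups. The rule should say what happens when the repeat does not confirm the rise and when no repeat is obtained. A cross-reference from the 6.7 sentence to 6.7.3.3 would keep the two aligned.

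Reword the shared threshold sentence so that each group has one reading, removing the tension between the control-only ULN limb and the whichever-is-greater clause.

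Which recording rule and which threshold apply are clinical decisions for the sponsor; this point takes no position on either. The cost is protocol wording only. No visit, sample or analysis changes, and the SAP tables would follow the single protocol rule as they stand.
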